7.3 Lost To Follow-Up

Participants who miss a study visit should be contacted to reschedule. If participants cannot be contacted immediately, attempts should continue until study completion. Lost to follow-up is defined as unsuccessful contact after at least two documented telephone calls and one written letter.

Any participant withdrawn from the study will not be replaced.

8 STUDY ASSESSMENT AND PROCEDURES

8.1 Screening and Efficacy Assessments

For all efficacy assessments and follow-up visits, refer to SoA ([Table 4](#)) for procedure to be done, and details below for each assessment.

8.1.1 Screening Procedures

After the informed consent, some or all of the following assessments are performed to determine eligibility requirements as specified in the inclusion and exclusion criteria:

- Confirm the positive SARS-CoV-2 test result.
 - If the original sample was >72 hours prior to planned randomization, an exception must be requested to the Sponsor.
- Take a focused medical history, including the following information:
 - Day of onset of COVID-19 signs and symptoms
 - History of chronic medical conditions related to inclusion and exclusion criteria
 - Medication allergies
 - Review medications and therapies for this current illness taken in the 7 days prior to Day 1 and record on the appropriate CRF.
- Women of childbearing potential should be counseled to either practice abstinence or use at least one primary form of contraception from screening through Day 60.
 - Acceptable forms of contraception include barrier methods, copper or hormonal IUDs, implantable hormonal contraception, or oral contraceptives.
 - Note: If a woman is either postmenopausal (i.e., has had ≥ 12 months of spontaneous amenorrhea) or surgically sterile (i.e., has had a hysterectomy, bilateral ovariectomy (oophorectomy), or bilateral tubal ligation), she is not considered to be of childbearing potential
- Obtain height and weight (height can be self-reported)
- Review results of recent radiographic imaging (x-ray or CT scan)
- Perform a targeted physical exam focused on lung auscultation
- Check a SpO2

- Obtain blood for screening laboratory evaluations if not done as part of routine clinical care in the preceding 48 hours:
 - type and screen
- Clinical screening laboratory evaluations will be performed locally by the site laboratory.
- The overall eligibility of the participant to participate in the study will be assessed once all screening values are available. The screening process can be suspended prior to complete assessment at any time if exclusions are identified by the study team.
- Study participants who qualify will be immediately randomized.

8.1.1.1 Screening Procedures in Pregnant Women

To best understand risk and benefit of study enrollment for pregnant women, we will follow this SOP for consideration of enrollment.

Standard Operating Procedure for Pregnant Patients:

1. Maternal Fetal Medicine (Obstetrical service managing pregnant patients) consults Infectious Diseases
2. Obstetrics (OB) and Infectious Diseases (ID) study physicians discuss possible enrollment in study, considering factors including fetal gestational age, maternal co-morbidities, severity of COVID-19 disease, volume status.
3. Discussion between OB, ID, patient (if possible) and patient legally authorized representative on risks and benefits of study.
4. With enrollment and plasma administration: close observation in acute setting (eg, in COVID-19 unit, ICU or Labor & Delivery)
5. Continue close monitoring after plasma administration. Participants will be followed through the 60 days of the study. Data will not be collected after the Day 60 visit nor will data be collected on neonates.

The volume of venous blood to be collected is presented in [Table 2](#).

8.1.2 Measures of clinical support, limitations and infection control

On each study day while hospitalized through Study Day 29, the following measures for the previous day will be recorded. i.e., on Day 3, Day 2 measures are assessed as occurring anytime in that 24 hour period (00:00 to 23:59h):

- Hospitalization
- Oxygen requirement
- Non-invasive mechanical ventilation (via mask) requirement

- High flow oxygen requirement.
- Invasive mechanical ventilation (via endotracheal tube or tracheostomy tube) requirement.
- ECMO requirement.
- Ongoing medical care preventing hospital discharge (COVID-19 related or other medical conditions)
- Limitations of physical activity (self-assessed).
- Isolated for infection control purpose

If drawn for clinical care, record inflammatory markers, including:

- Ferritin, C Reactive Protein, D-Dimer, Fibrinogen, Erythrocyte Sedimentation Rate, Triglycerides, IL-6.

If and when a participant is discharged from the hospital, they will continue with study visits as an outpatient, for all Study Days that are applicable, including Days 15, 29, and 60. Outpatient visits will involve the participant returning to clinic, unless other reasonable accommodations for evaluations and blood draws can be arranged. Day 22 Study visit can be as a phone call. Given the COVID-19 restrictions and the difficulty some of the participants might have to attend an in person visit after hospital discharge, the collection of Day 60 data for primary and secondary endpoints and the collection of Day 60 samples for exploratory tests may be performed up to 90 days following the Day 60 visit. For these participants, the Day 60 data may be obtained from the information already entered in the clinical records by any clinician, or by contacting the participant by phone up to 90 days following the Day 60 visit to obtain retrospective data.

8.1.3 *Ordinal Scale*

The ordinal scale is an assessment of the clinical status at the first assessment of a given study day. From the measures collected in 8.1.2.1, this ordinal scale can be constructed.

The scale used in this study is as follows:

1. Not hospitalized, no limitations on activities.
2. Not hospitalized, limitation on activities and/or requiring home oxygen;
3. Hospitalized, not requiring supplemental oxygen - no longer requires ongoing medical care;
4. Hospitalized, not requiring supplemental oxygen - requiring ongoing medical care (COVID-19 related or otherwise);
5. Hospitalized, requiring supplemental oxygen;

6. Hospitalized, on non-invasive ventilation or high flow oxygen devices;
7. Hospitalized, on invasive mechanical ventilation or ECMO;
8. Death

By assessing the individual components however, alternative scales can be constructed.

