3.2 Secondary Objectives and Endpoints

For the secondary objectives, we will compare treatment and control arms based on the following list of clinical endpoints which capture different aspects of disease severity.

OBJECTIVES	ENDPOINTS (OUTCOME MEASURES)

1. Evaluate the clinical efficacy of convalescent plasma administration by comparing treatment vs control arms
 
 • Clinical Severity 
 ○ Ordinal scale: 
 ■ Time to recovery, defined by time to levels 1-3 on the ordinal scale ■ Time to an improvement of one category and two categories from Day 1 using an ordinal scale. ■ Participant clinical status using ordinal scale at Days 3, 5, 8, 11, 15, 22, and 29. ■ Mean change in the ordinal scale from Day 1 to Days 3, 5, 8, 11, 15, 22, and 29. 	
 • Clinical outcome assessed using ordinal scale daily while hospitalized and on Day 15, 22, and 29. • Clinical status assessment (8-point ordinal scale) includes: 
 1. Not hospitalized, no limitations on activities. 2. Not hospitalized, limitation on activities and/or requiring home oxygen; 3. Hospitalized, not requiring supplemental oxygen - no longer requires ongoing medical care; 4. Hospitalized, not requiring supplemental oxygen - requiring ongoing medical care (COVID-19 related or otherwise); 5. Hospitalized, requiring supplemental oxygen; 6. Hospitalized, on non-invasive ventilation or high flow oxygen devices; 7. Hospitalized, on invasive mechanical ventilation or ECMO; 8. Death

 ○ National Early Warning Score (NEWS): 
 ■ Time to discharge or to a NEWS of ≤ 2 and maintained for 24 hours, whichever occurs first ■ Change from Day 1 to Days 3, 5, 8, 11, 15, and 29 in NEWS. 	
 • NEWS assessed daily while hospitalized and on Days 15 and 29.

 ○ Oxygenation: 
 ■ Oxygenation free days to Day 29. ■ Incidence and duration of new oxygen use during the study. 	
 ■ Days of supplemental oxygen (if applicable)

OBJECTIVES	ENDPOINTS (OUTCOME MEASURES)

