12 APPENDIX

12.1 Schedule of Activities (SoA)

The following page outlines all of the assessments to be conducted during the study. A detailed presentation of assessments immediately follows the table.

Table 4: Schedule of Activities

	Screen	Baseline	Study Period				
	While inpatient			While inpatient or as outpatient visits			
Day +/- Window	-1 or 1	1	Day 2 to 29	15 ⁷ ± 2	22 ⁷ ± 3	29 ⁷ ± 3	60 ⁷ ± 5 ¹⁰
ELIGIBILITY							
Informed consent	X						
Demographics & Medical History	X						
Targeted physical exam	X						
Review SARS-CoV-2 results	X						
STUDY INTERVENTION							
Randomization		X					
Administration of investigational plasma		X					
STUDY PROCEDURES							
Vital signs including SpO ₂		X ⁴	Daily until discharge or Day 29 of hospitalization	X		X	X
Clinical data collection ¹		X ⁴	Daily until discharge or Day 29 of hospitalization	X	X ⁸	X	X
Targeted medication review		X ⁴	Daily until discharge or Day 29 of hospitalization	X		X	X
Adverse event evaluation		X ⁴	Daily until discharge or Day 29 of hospitalization	X	X	X	X
SAFETY LABORATORY							
Type and Screen	X ^{2,3}						
Safety hematology, chemistry and liver tests		X ^{4,5,6}	Day 3, 5, 8, 11 (all ± 1 day) if hospitalized ^{5,6}	X ⁹		X ⁹	
Pregnancy test for females of childbearing potential	X ^{2,3}						
RESEARCH LABORATORY							
Oropharyngeal swab or endotracheal sample		X ⁵	Day 3, 5, 8, 11 (all ± 1 day) if hospitalized	X			

Blood for research		X ⁵	Day 3, 8, (all ± 1 day)	X		X	X
--------------------	--	----------------	-------------------------	---	--	---	---

1 Refer to [Section 8.1](#) of the protocol for details of clinical data to be collected including ordinal score, NEWS, oxygen requirement, mechanical ventilator requirement, etc.

2 Screening laboratory tests include: ALT, AST, creatinine (and calculate an estimated glomerular filtration rate (eGFR)), and pregnancy test.

3 Laboratory tests performed in the 48 hours prior to enrollment will be accepted

4 Baseline assessments should be performed prior to study drug administration. Laboratory tests performed as part of routine clinical care in the 24 hours prior to first dose will be accepted for the baseline safety laboratory tests. Baseline may be the same as the screening laboratory tests.

5 Safety laboratory tests include WBC with differential, hemoglobin, platelets, creatinine, glucose, total bilirubin, ALT, AST, and PT.

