6 Any laboratory tests performed as part of routine clinical care within the specified visit window can be used for safety laboratory testing. Window during the study period is ±1 day.

7 In-person visits are preferred but recognizing quarantine and other factors may limit the participant's ability to return to the site for the visit. In this case, these visits may be conducted by phone and blood and OP can be coordinated remotely.

8 Phone call at Day 22 is to assess clinical status (ordinal scale), adverse events, readmission to a hospital, and mortality only.

9 Safety laboratory tests on Day 15 and 29 if still hospitalized or returns to the site for the visit or at home visit.

10 The collection of Day 60 data for primary and secondary endpoints and the collection of Day 60 samples for exploratory tests may be performed up to 90 days following the Day 60 visit.

12.2 Division of AIDS (DAIDS) Table for Grading the Severity of Adult and Pediatric Adverse Events, Corrected version 2.1 (July 2017)

[Division of AIDS \(DAIDS\) Table for Grading the Severity of Adult and Pediatric Adverse Events \(Corrected Version 2.1 - July 2017\)pdf](#)

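### Oxygen use is not scheduled for capture between post-discharge contacts, so oxygen-free days to Day 29 cannot be validly counted for participants sent home on oxygen

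*Combined protocol and SAP*

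**What the plan says.** Section 3.2 lists "Oxygenation free days to Day 29" as a secondary endpoint, together with the incidence and duration of new oxygen use. The matching outcome measure is the number of days on supplemental oxygen; whether home oxygen counts is not stated, and no derivation is given.

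The data behind these endpoints come from three places:

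- **In hospital.** Section 8.1.2 sets the recording window as "On each study day while hospitalized through Study Day 29", with each entry covering the day before. Oxygen requirement is one of the listed measures. The Schedule of Activities (Section 12.1) gives the same window: "Daily until discharge or Day 29 of hospitalization".
- **Days 15 and 29, inpatient or outpatient.** The Schedule marks clinical data collection at these visits, and its footnote 1 describes this as "clinical data to be collected including ordinal score, NEWS, oxygen requirement, mechanical ventilator requirement, etc". Section 3.2 also has NEWS assessed on Days 15 and 29, and Table 1 scores any supplemental oxygen as yes or no.
- **Day 22.** Footnote 8 limits the contact: "Phone call at Day 22 is to assess clinical status (ordinal scale), adverse events, readmission to a hospital, and mortality only".

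Level 2 of the ordinal scale reads "Not hospitalized, limitation on activities and/or requiring home oxygen". The general missing-data rule in Section 9.4.1 is complete case, without replacement. Section 9.4.3 defers further detail on secondary endpoints to a SAP; no separate SAP text forms part of the combined document.

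**The concern.** A count of oxygen-free days needs the oxygen status of every day to Day 29. The plan supplies it daily up to discharge and then on two isolated days. The wording of level 2 shows that discharge on home oxygen is expected, and entry at ordinal levels 5 to 7 (Section 5.1) makes it plausible for some participants. Yet nothing in the documents dates when home oxygen starts or stops.

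The trial is open-label (Sections 4.2 and 6.3), so the timing and circumstances of discharge are decided with knowledge of allocation. If the arms differ in how often participants go home on oxygen, an endpoint that cannot see home oxygen may differ between arms for reasons other than oxygen need. Section 3.3 reuses the endpoint in the exploratory comparison with recipients of active drug in another protocol, where an undefined count would add a further source of incomparability.

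**Working it through.** The plan states no figure for this endpoint, so there is nothing to reproduce. The check is a count of days.

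**Step 1: days with no scheduled oxygen record.** Inputs: discharge day d (assumed), end of count Day 29, oxygen status scheduled at Days 15 and 29, ordinal level only at Day 22.

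Remaining days = 29 − d. Days with nothing scheduled = (29 − d) − (oxygen visits after d) − (Day 22, if after d).

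| Discharge day (assumed) | Remaining days | Oxygen status scheduled | Ordinal level only | Nothing scheduled |
|---|---|---|---|---|
| 5 | 24 | 2 | 1 | 21 |
| 8 | 21 | 2 | 1 | 18 |
| 11 | 18 | 2 | 1 | 15 |
| 15 | 14 | 1 | 1 | 12 |
| 22 | 7 | 1 | 0 | 6 |

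Day 22 helps in part: level 1 implies no home oxygen on that day, but level 2 leaves the question open.

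**Step 2: what each possible rule does to one participant.** Take discharge on Day 8 with home oxygen through Day 29 (assumed), after oxygen on every hospital day. The true number of oxygen-free days is 0.

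- Every post-discharge day counted as free, visit records ignored: 29 − 8 = 21 days wrongly credited.
- The same, but with the positive records at Days 15 and 29 used: 21 − 2 = 19 days wrongly credited.
- Unrecorded days left missing: no false credit, but the count is incomplete. This affects everyone discharged with unrecorded days before Day 29, on oxygen or not, so the loss depends on outcome.
- Home-oxygen days captured and counted as oxygen days: error 0.

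With home oxygen lasting only 7 days after a Day 8 discharge, the first rule gives an excess of 7 days (21 credited against a true 14).

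**Step 3: effect on the comparison.** If unrecorded days are counted as free and visit records are not used:

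shift in mean difference = (share on home oxygen in one arm − share in the other) × days of home oxygen per user

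The documents give neither input. Assuming 14 days per user:

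- equal shares: 0 × 14 = 0 days;
- a 10-percentage-point difference (4 of 40 participants): 0.10 × 14 = 1.4 days;
- a 20-percentage-point difference (8 of 40): 0.20 × 14 = 2.8 days.

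Section 9.4.3 compares continuous endpoints by Wilcoxon rank-sum, so these shifts describe the reported means and do not translate directly into the test.

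**The case against.** A reader might infer that the plan will credit home-oxygen days as oxygen-free and so reward discharge on oxygen. The documents do not support that. No section says that unrecorded days count as free, and the default in Section 9.4.1 does not fill in missing values. False credit is one possible outcome of an unwritten rule.

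Nor is oxygen status lost altogether after discharge. Footnote 1 of the Schedule and the NEWS oxygen item make it obtainable at Days 15 and 29 and, on those days, separate home oxygen from activity limitation. The case report form is not in the documents, so they cannot show that no dates are collected, only that none are specified. A later SAP may also contain a derivation rule.

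The endpoint is also not among the key secondary endpoints (survival and time to recovery), in an 80-participant phase 1 trial with mainly descriptive analyses.

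All of this stands and limits the point. It does not close the gap. Two visit records do not give a day count, and a SAP can define how to count days but cannot supply dates that were never asked for. Section 8.1.2 does allow Day 60 data to be gathered retrospectively from clinical records or by phone, but it names no oxygen dates among them.

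**Conclusion.** The point holds as a gap in data capture combined with an undefined derivation. Followed as written, the plan cannot give a valid day count for oxygen-free days to Day 29, or for duration of new oxygen use, in participants sent home on oxygen. In the illustrated discharges from Day 5 to Day 22, between 6 and 21 post-discharge days have no scheduled oxygen record. The individual error depends on the unwritten rule: for the Day 8 case it runs from 0 to 21 days, the upper end requiring that the visit records be ignored too.

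A bias between arms is not established. It needs unequal home-oxygen use, on which the documents are silent; the 1.4-day figure rests on an assumed 10-percentage-point difference and 14 days per user, and equal use gives 0. The consequence is modest: a secondary endpoint becomes hard to interpret, while the primary endpoints are unaffected by this point.

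**What to change.** In Section 8.1.2 and the Schedule of Activities, add home oxygen (yes or no), with start and stop dates since the last contact, at Days 15, 22 and 29. Footnote 8 must be widened so that the Day 22 call may ask it. State with the endpoint definition that home-oxygen days are not oxygen-free.

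The yes/no part is already largely available at Days 15 and 29, so the real additions are the dates and the Day 22 item. The cost is one short question at contacts that already take place, and a slight recall error in the dates. This is a cheap improvement.

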5 STUDY POPULATION

5.1 Inclusion Criteria

1. Adult ≥ 18 years of age
2. Laboratory-confirmed SARS-CoV-2 infection as determined by PCR or other authorized or approved assay in any specimen collected within 72 hours prior to enrollment.

Note – An exception must be requested to the Sponsor if ≥ 72 hours since positive test.

3. Hospitalized in participating facility.
4. Documentation of pneumonia with radiographic evidence of infiltrates by imaging (e.g., chest x-ray or CT scan).
5. Abnormal respiratory status that is judged worse than baseline by the investigator and as documented at any point within 24 hours prior to randomization, consistent with ordinal scale levels 5, 6 or 7, specifically defined as:
 - Room air saturation of oxygen (SaO_2) $< 93\%$, OR
 - Requiring supplemental oxygen, OR
 - Tachypnea with respiratory rate ≥ 30
6. Patient or proxy is willing and able to provide written informed consent and comply with all protocol requirements

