6.3 Measures to Minimize Bias: Randomization and Blinding

Individuals will be randomized to the intervention or control arm in a 1:1 ratio. Randomization will occur in a blinded fashion using Redcap. Allocation will be determined using a permuted block algorithm with varying block sizes. We will stratify randomization based on whether or not a patient is on mechanical ventilation and on [remdesivir](#) at baseline. Though the intervention will not be blinded, we will attempt to minimize bias by blinding study personnel, such as individuals running laboratory assays, to the extent that it is possible.

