8.1.4 National Early Warning Score (NEWS)

NEWS has demonstrated an ability to discriminate participants at risk of poor outcomes. (Smith, 2016). This score is based on 7 clinical parameters (see [Table 1](#)). The NEWS is being used as an efficacy measure. This should be evaluated at the first assessment of a given study day and prior to administration of study product. The 7 parameters can be obtained from the hospital chart using the last measurement prior to the time of assessment and a numeric score given for each parameter (e.g., a RR of 9 is one point, oxygen saturation of 92 is two points). This is recorded for the day obtained. i.e., on Day 3, Day 3 score is obtained and recorded as Day 3.

Table 1: National Early Warning Score (NEWS)

PHYSIOLOGICAL PARAMETERS	3	2	1	0	1	2	3
Respiration Rate	≤8		9 - 11	12 - 20		21 - 24	≥25
Oxygen Saturations	≤91	92 - 93	94 - 95	≥96			
Any Supplemental Oxygen		Yes		No			
Temperature	≤35.0		35.1 - 36.0	36.1 - 38.0	38.1 - 39.0	≥39.1	
Systolic BP	≤90	91 - 100	101 - 110	111 - 219			≥220
Heart Rate	≤40		41 - 50	51 - 90	91 - 110	111 - 130	≥131
Level of Consciousness				A			V, P, or U

Level of consciousness = alert (A), and arousable only to voice (V) or pain (P), and unresponsive (U).

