8.4.8 Events of Special Interest

There are no events of special interest in this protocol.

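### A Grade 1-2 transfusion-associated volume overload falls outside the reported safety set; make it and TRALI reportable at any grade

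*Combined protocol and SAP*

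**What the plan says.** **Named harms.** Section 2.3.1.1 lists TRALI and, for the roughly 500 mL in two units, volume overload leading to pulmonary edema. Section 4.3 lets the principal investigator give one unit where overload is a concern, and 5.2 excludes patients with severe volume overload.

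**What is reported.** The trial-specific rule in 8.4.4 covers Grade 3 and 4 AEs and all SAEs from consent to Day 60. It adds one exception, hypersensitivity reactions of any grade. The safety endpoints in 9.4.4 are death, SAEs, infusion discontinuation and Grade 3-4 AEs, and the secondary safety endpoint in 3.2 also counts only Grade 3 and 4. Section 8.4.8 adds: "There are no events of special interest in this protocol".

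**Text that points the other way.** Earlier in 8.4.4, all adverse events go into the source documents. Section 8.4.5.2 asks for all AEs on the CRF. Sections 9.4.4 and 9.4.6 pause the study for transfusion reactions, without a definition or a grade.

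**Ventilated participants.** Eligibility is "consistent with ordinal scale levels 5, 6 or 7", and section 6.3 says "We will stratify randomization based on whether or not a patient is on mechanical ventilation". The daily measures in 8.1.2 include "Invasive mechanical ventilation (via endotracheal tube or tracheostomy tube) requirement". Footnote 1 of the Schedule of Activities refers to "clinical data to be collected including ordinal score, NEWS, oxygen requirement, mechanical ventilator requirement, etc". The NEWS oxygen item is "Any Supplemental Oxygen", scored yes or no, and ordinal level 7 is "Hospitalized, on invasive mechanical ventilation or ECMO".

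**The concern.** A phase 1 plasma trial should be able to say how well two units were tolerated. Volume overload is a foreseeable harm of the dose and bears on the choice between one and two units. Under the reporting rule, a low-grade case need not be reported and has no place among the safety endpoints. The protocol already makes an any-grade exception for one class of infusion harm but not for the two lung-related transfusion harms it names. Because 8.4.4 and 8.4.5.2 disagree on scope, staff could record low-grade cases for some participants and not for others.

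A related but lesser matter is that, once a participant is ventilated, the listed daily measures do not show how much oxygen is being given. A brief decline after infusion could pass without a change in any of them.

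**Working it through.** **1. Reporting scope, section by section.** Take a Grade 2 volume overload in the plasma arm that does not prolong hospitalization and does not stop the infusion.

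- 8.4.4 reporting rule: not Grade 3-4, not an SAE, not hypersensitivity, so not required.
- 8.4.8: no event of special interest, so no separate route.
- 9.4.4 and 3.2 endpoints: not counted.
- 8.4.4 source-document sentence and 8.4.5.2 CRF sentence: recorded, if these override the trial-specific rule. The text does not say which governs.
- Pause trigger: may or may not apply, since transfusion reactions are undefined. If it applies, it prompts DSMB review and does not put the event in the tables.

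**2. Size, using the protocol's own table.** Table 3 gives Pr(at least one event) = 1 - (1 - p)^40. At p = 0.04 this is 1 - 0.96^40 = 0.805, against the stated 0.80; all eight rows reproduce. No overload rate is given, so assume a rate p and a share c of cases that meets the reporting threshold. Then Pr(at least one reported) = 1 - (1 - pc)^40:

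| Assumed p | c = 1 | c = 0.75 | c = 0.5 | c = 0.25 |
|---|---|---|---|---|
| 0.02 | 0.554 | 0.454 | 0.331 | 0.182 |
| 0.04 | 0.805 | 0.704 | 0.554 | 0.331 |
| 0.10 | 0.985 | 0.956 | 0.871 | 0.637 |

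For TRALI the only rate given is 1 in 5000 transfusions, before mitigation. With at most 40 × 2 = 80 units, each counted as one transfusion, 1 - (1 - 1/5000)^80 = 0.016. The any-grade rule would therefore act mainly on volume overload.

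**3. The FiO2 point.** Assumed values for a ventilated participant, scored from Table 1 in the order respiratory rate 18, SpO2 94%, on oxygen, 37.0 C, systolic BP 115, heart rate 88, not alert: 0+1+2+0+0+0+3 = 6. FiO2 does not enter the score, so with SpO2 held at 94% NEWS stays 6 and the ordinal level stays 7:

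| FiO2 | SpO2/FiO2 | Change from 0.40 |
|---|---|---|
| 0.40 | 94/0.40 = 235 | - |
| 0.50 | 94/0.50 = 188 | -20% |
| 0.60 | 94/0.60 = 157 | -33% |
| 0.90 | 94/0.90 = 104 | -56% |

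NEWS does respond when other items change. SpO2 of 90% gives 0+3+2+0+0+0+3 = 8. Systolic BP 88 with 38.5 C gives 0+1+2+1+3+0+3 = 10. Adding heart rate 115 gives 12.

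**4. Precision of an SpO2/FiO2 comparison.** The 95% CI half-width for the arm difference, in SD units, is t(0.975, 2n-2) × sqrt(2/n). The number ventilated is not stated. With an assumed 10, 20 or 30 per arm it is 0.94, 0.64 or 0.52 SD; with all 40 per arm it is 0.45 SD.

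**The case against.** A reader might infer that lung injury in a ventilated participant, short of ECMO or death, is seen only if staff who know the arm call it an AE. The documents do not support this. Ventilator/ECMO-free days, duration of hospitalization, time to recovery and the ranked severity score are all compared by randomised arm, and worsening that prolongs support moves them without any AE call. TRALI with hypotension and fever would move NEWS. What remains uncovered is a brief decline that does not prolong support.

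A reader might also infer that respiratory events are not summarised. That is too strong: 9.4.4 presents AEs by system organ class, and SAEs are also broken down by preferred term.

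Nor is it established that low-grade overload goes uncollected. The all-AE sentences may bring it onto the CRF. An overload that stops the infusion is counted as a discontinuation, and one that prolongs hospitalization is an SAE whatever its grade. The synopsis plans an assessment 30 minutes after each unit, and 6.1.2 adds an hour between units and an hour of observation afterwards. These checks help detect an event but do not settle whether a Grade 1-2 event is reported and tabulated.

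A large rise in FiO2 may well qualify as Grade 3 under the general definitions in 8.4.3.1. The DAIDS table is linked, not reproduced, so this cannot be checked. The CRF is not in the documents and footnote 1 is open-ended, so FiO2 may already be collected. NEWS is labelled an efficacy measure, and whether to add an oxygenation measure to a descriptive 80-person trial is open to reasonable debate.

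**Conclusion.** The point holds as a gap in reporting scope. As written, a Grade 1-2 volume overload that is not serious and does not stop the infusion is outside the reported and analysed safety set, although the protocol names volume overload as a plasma risk. The conflict with the all-AE sentences makes its handling uncertain; it does not show that the data will be lost. The size depends on two quantities the documents do not give, the overload rate and the share below the threshold. At an assumed 4% and one half, the chance of reporting at least one case in 40 falls from 0.80 to 0.55.

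The FiO2 observation is correct but secondary. It concerns short-lived declines in ventilated participants in whom SpO2 and the other NEWS items hold steady. It does not show that the plan is blind to lung harm in this group.

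**What to change.** **Recommended.** In 8.4.4 and 8.4.8, make TRALI and transfusion-associated volume overload reportable at any grade, as hypersensitivity already is, and state that this rule governs over the general all-AE sentences for these events. In 9.4.4, list both events by arm and grade. The cost is a sentence or two and a few extra AE records. These records will still rest on unblinded judgement and, since controls receive no study infusion, will arise only in the plasma arm. The listing is descriptive and is not a randomised comparison.

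**Optional.** If FiO2 is not already on the CRF, take it with a simultaneous SpO2 from the chart in both arms on Days 1-3. NEWS already uses the chart: "The 7 parameters can be obtained from the hospital chart using the last measurement prior to the time of assessment". The NEWS reading is at the first assessment of the day, so after a pre-infusion Day 1 value the next would be on Day 2. Add a reading within hours of infusion, at a matched time in controls. Tabulate change in SpO2/FiO2 by randomised arm in the ventilated stratum, with deaths and new ECMO alongside. Four readings (Day 1 before and after infusion, Day 2, Day 3) are at most 4 × 80 = 320 FiO2 values if every participant is included, and fewer if only ventilated participants are. No new visit or blood draw is needed. FiO2 is set by clinicians who know the arm, much of the change will be COVID-19 course, and the estimates will be imprecise, so the table would supplement AE reporting and not replace it.
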